Expanding clinical indications and an aging population have resulted in an increased number of implanted cardiac devices (CIEDs) being used worldwide. CIEDs record patient activity (PA) on a daily basis in addition to other physical parameters. Despite routine use in clinical practice, the utility of integrated PA diagnostics to monitor health in an older population remains relatively unexplored. This novel, interdisciplinary study aims to utilise easily accessible data from CIED downloads to improve our understanding of the relationship between PA and major health events (as measured by non-elective hospital attendance episodes) in an older population with heart disease. The PATTErn study will recruit 150 people aged ≥ 60 years with a CIED from the Manchester University NHS Foundation Trust over an 18-month period. Their observational data will be analysed to explore longitudinal PA patterns, correlations with markers of physical ageing such as frailty, and the relationship between PA and non-elective hospital attendance episodes (NEHAs). In essence, this study will bring together expertise in Geriatric Medicine and Cardiology, to exploring how this 'non-cardiac' device data correlates with health status.

Results will directly guide local pilot studies testing the impact of personalised, actionable clinical summaries from CIED data downloads. It will also have wider impact across the research community, accelerating our knowledge of the interaction between PA and health outcomes in an older cohort. This may lead to future projects looking at the use of this data to proactively identify older people at immediate risk of hospitalisation.

Research question

What are the normal variations in daily PA in later life, and how does PA associate with major health events?

Aims

1. Describe the relationship between PA and NEHAs in an older CIED cohort
2. Describe daily variability of PA in an older CIED cohort
3. Describe the relationship between PA and NEHAs, and examining whether frailty moderates this relationship

4. Confirm/refute the clinical observation that a drop in PA tends to precede episodes of NEHA in later life, and if so, evaluate predictive value

Method

Study Type: observational, investigator led

Study Design: observational model: cohort (retrospective)

Population: 150 people over 60 years of age with a Medtronic CareLink® compatible CIED in situ recruited from the Manchester University NHS Foundation Trust, England, UK

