Data collection: daily PA measures, demographic details, co-morbidity status, physical frailty assessment, functional status, quality of life (QOL) and NEHA data

Consent: for participation in the study, physical frailty assessment, additional collection of retrospective CIED data, and access to electronic patient records

Data sources: CIED downloads, self-report questionnaire, physical measurements (height, weight, hand grip strength, gait speed), electronic hospital records, HES (hospital episode statistics) data

Results analysis: data will be analysed to investigate: daily PA variability; the association between PA and NEHAs, and the impact of frailty on PA patterns

Scientific and medical opportunities

This study will collect a unique set of new data for analysis. Combining expertise in Geriatric Medicine and Cardiology, this work will aim to provide a scientific basis for some of the fundamental assumptions made regarding health behaviours in later life. Little is known about normal day-to-day fluctuations in PA in an older population. This objective data will shed light on these patterns, and the temporal relationship between PA and NEHAs. Not only will this enhance our clinical knowledge, but it will provide the opportunity to develop proactive monitoring systems – potentially using PA as a proxy marker of health in certain older patient groups.

Expected outcomes

This study expects to find that NEHAs are commonly preceded by a demonstrable acute decline in PA. Various models will be tested to demonstrate predictive validity. This association is expected to vary by patient sub-groups defined by baseline health status (co-morbidity burden, degree of frailty), and demonstrated underlying activity pattern.

Further avenues for research

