Every day, a huge volume of physiological data, including daily PA, is routinely collected by most modern cardiac implantable electronic devices (CIEDs). These devices are fitted in patients with cardiac conduction disorders and/or heart failure (HF). The average age of a patient undergoing implantation of a CIED in the UK is approximately 70 year old (14, 15). Older people with CIEDs are a cohort of patients with a particularly high risk of clinical frailty, hospitalisation and mortality (16-19). This therefore makes an ideal population to study PA patterns and temporal relationships with major health events.

CIED remote monitoring

Modern CIEDs continuously collect data for a host of physiological parameters relevant to cardiac function, including; heart rate, rhythm and variability, thoracic impedance, pacing time and PA. This data is stored within the device until it is ‘downloaded’ for analysis (for up to 14 months). For example, the Medtronic CareLink® Network allows patients to manually download data via a home monitor system as well as automatic programmed downloads ordered by clinicians (usually every 3 months from home, and an annual hospital based CIED check). Reports are then forwarded on to care providers for action. PA is considered ‘low’ if patients are ‘active’ (defined as >70 steps/min) for less than 60 minutes over a 1-week period (non-overlapping).

Existing evidence

Algorithms using CIED data to predict impending healthcare utilisation (HCU) have been in existence for a number of years, but are not yet integrated into standard UK clinical practice. The PARTNERS-HF study (20) tested a prediction algorithm based on a combination of 8 parameters (AF duration, ventricular rate during AF, fluid index, patient activity, night heart rate, heart rate variability, % of pacing CRT and ICD shocks) in HF patients with CRT defibrillators. Patients with parameters outside the norm for 2 or more domains triggered an alert for clinical action. Cowie *et al.* 2013 expanded the PARTNERS-HF dataset, totalling 921 HF patients, mean age 67-68 years (21). 30-day HF hospitalisation rates in the high-risk group were 10 times higher than in the low risk groups, HR (hazard ratio): 10.0; 95% CI: 6.4–15.7, P, 0.001. ‘Low’ versus ‘high’ PA was the most common domain trigger, contributing to over 80% of high-risk alerts. Low PA as a single domain was associated with a 2-3 fold increased risk of HF hospitalisation (HR 2.5, P<0.001).

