Stroke/TIA	
 • Self-report • Coded on electronic medical records

	
• Brain imaging demonstrating previous ischaemic or haemorrhagic event
--	--

Withdrawal from Study

All participant derived data will be collected on the day of consent, bar the occasional case where a participant wishes to take the questionnaire home and post in back at a later date. Given the short period of time each participant will be actively enrolled in the study, it is highly unlikely a withdrawal of consent will occur. In the event of withdrawal of consent, a consent withdrawal form will be used to document this event. All data collected up to the date of consent withdrawal will be retained, but no further outstanding data collected. This will be made clear in the study information and consent form.

Statistical Analysis

Basic variables from CIED data

CIED data will be processed to create a new set of basic variables for analysis.

1. Mean daily physical activity (MDPA) – mean PA across dataset
2. PA intra-individual variability – as measured by:
 - Range
 - Interquartile range
 - Mean absolute deviation
3. PA surrounding NEHAs – multiple measures.

DOEDA = date of emergency department attendance; DOA = date of hospital admission; DOD = date of discharge; LOS = length of stay (DOD-DOA)

- Difference in PA from MDPA on DOEDA/DOA day -1, day -2, day-3, day-7, day -14
- Difference in PA from MDPA on DOEDA/DOD day +1, day +2, day+3, day+7, day +14
- ‘Time till PA recovery’ – time from DOEDA/DOD to day regained \geq MDPA

Descriptive analyses

All data will be stored and analysed using SPSS and ‘R’ statistical computing software. Basic descriptive statistics will be used to compare different sub-groups of participant (e.g. frail v non-frail). MDPA will be used to facilitate basic comparative analysis using a continuous variable. Determinants of MDPA will be calculated using univariate and multivariable analysis.

PA patterns

As demonstrated in *Figure 3* below, common activity patterns embedded within CIED PA data will be identified using clustering algorithms. Using these identified subtypes of PA as exposures in a longitudinal model with outcome NEHA, multilevel/hierarchical modelling methods (both classical and Bayesian approaches) will be utilised to investigate associations with outcome.

[figure not shown]

Figure 3

PA and major health events

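### Objective 2 asks for daily variability of PA, but the three listed measures ignore the order of days and state no window, so slow change is mixed in

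*Combined protocol and SAP*

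**What the plan says.** Aim 2 in the Summary, repeated as item 2 of Study Objectives, is "Describe daily variability of PA in an older CIED cohort". The Summary gives the motive under Scientific and medical opportunities: "Little is known about normal day-to-day fluctuations in PA in an older population". Its Method paragraph on results analysis says "data will be analysed to investigate: daily PA variability".

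The operational definition is in Statistical Analysis, Basic variables from CIED data. Item 2, "PA intra-individual variability", lists the range, the "Interquartile range" and the "Mean absolute deviation". It gives no window, detrending, seasonal term or measure based on consecutive days, and does not say what the deviation is centred on. Item 1, mean daily PA (MDPA), is defined as "mean PA across dataset". Under CIED remote monitoring, the device is said to store data "for up to 14 months".

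The text on PA patterns clusters participants' activity patterns and uses the resulting subtypes as exposures for non-elective hospital attendance. It does not link the clusters to the variability measures.

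**The concern.** The objective is about how much a person's activity moves from one day to the next. The listed measures describe how widely the daily values are spread, whenever they occurred. Over a few weeks the two are nearly the same. Over a year they need not be: a participant whose activity shifts slowly but is steady from day to day can have the same IQR as one with a constant level and large daily swings.

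At stake is the interpretation of objective 2. A description of normal daily fluctuation would be too wide by an unknown amount, differing between participants. The same mixing would affect any comparison of variability between subgroups, such as frail and non-frail, if the groups differ in slow change. Nothing in the plan would show whether a difference came from daily fluctuation or from drift.

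**Working it through.** The plan states no figure for objective 2, so there is none to reproduce. Table 1 concerns the sample size for a different question and has no bearing here.

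**Inputs.** From the documents: the three measures, the whole-dataset window of MDPA, and storage of up to 14 months. Assumed, because the documents give no values: daily SD 15 or 30 min; linear decline of 40, 60 or 80 min over about a year; annual swing of ±15 or ±30 min; independent normal daily noise.

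**Step 1: order.** Shuffling the days of one simulated declining record (60-min decline, daily SD 30) leaves range 190.7, IQR 48.9 and MAD 28.0 unchanged. The SD from successive differences, √(mean(d²)/2), rises from 29.3 to 34.8. The invariance is exact and needs no assumption about patients.

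**Step 2: drift with no daily noise.** A linear decline of D minutes gives range D, IQR D/2 and MAD D/4. For D = 60 these are 60, 30 and 15, although the successive-difference SD is only 0.12.

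**Step 3: drift plus noise.** With daily SD σ, the whole-record SD is √(σ² + D²/12) for a linear decline and √(σ² + A²/2) for a swing of ±A.
- σ = 30, D = 40: √(1 + 1600/10800) = 1.07
- σ = 30, A = 15: √(1 + 112.5/900) = 1.06
- σ = 15, D = 60: √(1 + 3600/2700) = 1.53

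Simulated means for IQR and MAD (364 or 365 days, 1,000 to 2,000 records per scenario):

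| Daily SD | Slow component | IQR | MAD | Inflation (IQR, MAD) |
|---|---|---|---|---|
| 15 | none | 20.2 | 11.9 | 0 |
| 15 | 40-min decline or ±15 swing | – | – | about 24% to 30% |
| 15 | 60-min decline | 32.9 | 18.7 | 64%, 57% |
| 15 | ±30 swing | 39.8 | 21.7 | 97%, 82% |
| 15 | 80-min decline | 41.4 | 22.9 | 106% (unrounded), 92% |
| 30 | none | 40.3 | 23.9 | 0 |
| 30 | 40-min decline or ±15 swing | – | – | about 6% to 7% |
| 30 | 60-min decline | 47.0 | 27.7 | 17%, 16% |
| 30 | ±30 swing | 50.7 | 29.6 | 26%, 24% |
| 30 | 80-min decline | 52.2 | 30.5 | 29%, 28% |

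The mean absolute successive-day difference stays at about 16.9 (SD 15) or 33.9 (SD 30) whatever the drift. In the scenarios also run at 425 days, the results were close to these.

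**Step 4: does a 28-day block remove the drift?** An 80-min decline over 364 days moves 80 × 28/364 = 6.2 min within a block. With σ = 15 the within-block SD becomes √(225 + 6.2²/12) = 15.1, under 1% too high. A ±30 swing changes fastest at 2π × 30/364 = 0.52 min per day, or 14.5 min per block. In that steepest block the SD is √(225 + 14.5²/12) = 15.6, about 4% too high; averaged over blocks it is less. Simulated within-block MAD stays essentially at its no-drift value.

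**Step 5: correlated days.** The mean absolute successive difference is 2σ√((1 − ρ)/π) for lag-1 correlation ρ. With σ = 30 it is 33.9 at ρ = 0 and 23.9 at ρ = 0.5, a fall of 29% with the same daily SD. Whole-record IQR (40.2) and MAD (23.8) barely move, and within-block MAD changes by about 4%.

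**The case against.** The best defence is that objective 2 is descriptive, and that the spread of a person's daily values is a legitimate description of variability. The item is labelled intra-individual variability, long-term shape is handled by clustering, and the figure illustrating the patterns is not available here. No window is stated for item 2, so a whole-record reading is an inference. Daily data are retained, so another measure could be derived later. Successive differences also have a weakness of their own, shown in step 5.

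Much of this stands. The measures are incomplete rather than invalid, the window is unstated rather than known to be the full record, and successive differences should not be the sole replacement. What does not stand is that clustering covers the gap: the text uses it to form exposures, not to separate slow change from daily spread.

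Three stronger readings are tempting but unsupported:
- A reader might infer that the protocol expects steady decline, or that frail participants decline most. The Context and Frailty sections describe vulnerability to decline after minor stressors. Seasonal change is not mentioned, and no decline rate by frailty is given.
- A reader might infer that alert thresholds would be set from an inflated spread. The plan uses differences from MDPA and a nested case-control comparison of trends for that purpose, not range, IQR or MAD.
- A reader might take a doubling as typical. It needs large drift together with small daily noise.

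**Conclusion.** The point holds as a mismatch between objective 2 and its measures. That range, IQR and MAD ignore order is exact. That they would be computed over the whole record is the natural reading beside MDPA, but the plan does not say so. Under that reading slow change inflates the measures; it is not all they report.

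The size depends on drift relative to daily noise, and the documents give neither. Over the assumed values, IQR and MAD rise by about 6% to 7% at the low end (40-min decline or ±15-min swing, daily SD 30). At the high end (80-min decline, daily SD 15), IQR rises by about 106% and MAD by about 92%. Without drift there is no inflation. It would go too far to say that the study cannot address normal variation in daily PA. As written, the plan does not isolate the daily part, and a measure that does so is cheap.

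**What to change.** In item 2 of Basic variables from CIED data:
- State the window for every variability measure and the centre used for the mean absolute deviation.
- Keep range, IQR and MAD, labelled as total within-person spread.
- For objective 2, add IQR and MAD calculated within consecutive 28-day blocks and averaged over blocks, and say how an incomplete block is handled. A 28-day block holds each weekday four times, so blocks are comparable.
- Report the mean absolute successive-day difference as a companion.

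The cost is one or two extra derived variables from daily PA already collected, with no added burden on participants. The limits should be stated: within-block spread still contains the drift inside each block (step 4), while successive differences shrink when neighbouring days are correlated and include the contrast between weekdays and weekends.

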CIEDs include pacemakers, implantable cardiac defibrillators (ICDs), and cardiac resynchronisation devices (CRT). NICE guidelines (National Institute for Health and Care Excellence) recommend CRT device implantation as a *treatment option* for HF patients with prolonged QRS interval on electrocardiogram and an ejection fraction of 35% or less (37). CRTs have been shown to improve symptoms and slow progression of HF in randomised control trials (RCT) (38, 39). The MIRACLE study (38) (an RCT of 453 patients with moderate to severe HF randomised to CRT versus medical therapy) demonstrated CRT patients experienced a median change in 'distance walked in 6 minutes' of +39m at 6-month follow up (median: +39m, 95% CI +26 to +54, compared to control median: +10m 95% CI 0 to +25, where CI = confidence interval). Evidence suggests the additional endurance effect of CRTs is diminished by 12 weeks of implantation (40), thus data from this time period will be excluded from analysis as PA data may not represent normal behaviour. This will also allow time for the

patient to recover from the procedure, and allow the device time to synchronise its settings. It is unclear how pacemaker or ICD implantation would affect PA, however one could expect some positive impact through better control of symptoms, or perhaps a psychological 'safety-net' for a more active lifestyle. Although some devices with tight pacing settings may limit exertion. We expect this impact to be very small.

Validity of frailty assessments

The Fried phenotypic based frailty assessments are well validated in the general population. We estimate over half of the patients recruited into the PATTERn study will have some degree of HF. One domain of frailty that may be less reliable in a HF cohort is weight loss – as this may fluctuate with fluid status. Significant weight loss within the criteria is defined as over 10% body weight in the preceding four years (or a measured BMI $< 18.5 \text{ kg/m}^2$). These criteria would not tend to capture patients whom have lost weight simply due to diuresis, therefore we do not anticipate this will alter validity of results. The Fried criteria have been used in a number of studies which include participants with HF (19, 41). The original validation study itself included patients with HF, who represented 4.5% of the original Cardiovascular Health Study cohort (42). Therefore, this assessment has validity in this context.

Generalisability of results

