By the nature of this study, participants are limited to those with a compatible CIED i.e. have some form of cardiac disease (the majority HF and/or conduction disorders). Cardiovascular disease is a fundamental pillar of ageing, lying on the spectrum of physiological frailty – inherent, and relevant to all older people (43). Therefore, on balance we do believe this population sample is generalisable to an older population with comparable functional status and degree of frailty. This study will be looking at temporal pattern analysis, using this population as a cohort of older people with a common age-associated long-term condition (heart disease). There is no reason to expect this group of patients would behave any differently with regard to PA and major health events compared with any other older patient group. Therefore we believe these results will be of interest out with the cardiac community.

Sample Size Calculations

Using data from previous analyses (21, 22) sample size calculations have been performed based on the Kesley and Fleiss formulas for 'cohort studies', using exposure = low/decline in PA and outcome = NEHA within 6 weeks. We considered a relative risk (RR) of 2.5-3 to be clinically significant in terms of a PA trigger signifying increased risk of NEHA. Sample size estimate thus = **150** participants (using inputs: 95% significance, 80% power, RR 2.5-3, output: 88 – 198, see *Table 1*).

Table 1: Sample size calculations

Variables	Option 1	Option 2	Option 3	Option 4
Two-sided significance level (1-alpha)	95	95	95	95
Power (1-beta, % chance of detecting):	80	80	90	90
Percent of Unexposed with Outcome:	17	17	17	17
Percent of Exposed with Outcome:	43	51	43	51
RR	2.5	3	2.5	3
Ratio of sample size, unexposed/exposed:	4.4	4.4	4.4	4.4
Sample size: Kesley	133	81	177	108
Sample size: Fleiss	145	88	198	121

The SENSE HF study (enrolling adult patients with chronic, stable HF, 6 months follow-up) captured 224 'unscheduled hospital visits' in 132 patients over 659 patient years, i.e. an annual rate of 34%. (44) Using this as a guide, with a sample size of 150 (150 patient years) we would expect to capture approximately 51 NEHA episodes from retrospective data collection.

Study Objectives

1. Describe the relationship between PA and NEHAs in an older CIED cohort
2. Describe daily variability of PA in an older CIED cohort
3. Describe the relationship between PA and NEHAs, and examining whether frailty moderates this relationship

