4. Confirm/refute the clinical observation that a drop in PA tends to precede episodes of NEHA in later life, and if so, evaluate predictive value

Study Design

Type

Observational study

Setting

Manchester University NHS Foundation Trust (MFT). This includes the trust's 2 main sites: Manchester Royal Infirmary and Wythenshawe Hospital.

Duration of Study

18 months

Participants

Inclusion/exclusion criteria are shown below, with reference to *Table 2* that lists compatible CIEDs for this study.

Inclusion Criteria

1. Age 60+ years
2. Functioning CIED in situ for at least 6 months
3. Medtronic manufactured device compatible with CareLink® Cardiac Compass application (platform which measures and stores physiological parameters)
4. Lives in the Greater Manchester area
5. Able and willing to give written, informed consent to enter the study

Exclusion Criteria

1. Faulty or incompatible device
2. Immobile (unable to walk in upright position)
3. Active participant in a clinical trial which does not allow concurrent recruitment into this study
4. People unable to consent in the English language (including the understanding of study literature which is published in English only)

Patients may be entered into registries, observational studies or clinical trials while also participating in PATTern.

Justification of Study Design

Study design

Research question: what are the normal variations in daily PA in later life, and how does PA change surrounding major health events?

This question is best answered by an observational study, as we are attempting to establish normal patterns of behaviour. Measuring PA using sensor devices allows for the passive collection of objective data. The use of retrospective PA data from CIED devices minimises participation bias (i.e. inadvertently influencing behaviour). Using a cohort of older people with CIEDs limits analysis to a particular cohort of older people, however as explained below in the 'generalizability of results' section, this analysis will still be of great value, and on the whole generalizable to the broader population. Specific considerations related to the PATTErn study are discussed in more detail below.

Selection Bias

Selection bias will be introduced by our inclusion/exclusion criteria and recruitment method in the following ways:

1. Inclusion criteria
 - 1.1. compatible CIED in situ
 - 1.1.1.The most frail patients would not be eligible/suitable for CIED implantation

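### Of the three planned measures of within-person PA variability, range alone depends materially on record length, and the plan sets no common observation window

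*Combined protocol and SAP*

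**What the plan says.** Study Objectives, item 2, is to "Describe daily variability of PA in an older CIED cohort". The derived variables that serve it are in Statistical Analysis, Basic variables from CIED data, under "PA intra-individual variability". Three are listed: range, "Interquartile range" and "Mean absolute deviation". None is named as the main one.

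Three other places determine how many days of PA a participant contributes:

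- Inclusion Criteria, item 2: "Functioning CIED in situ for at least 6 months".
- Impact of CIED implantation on results: the extra endurance effect of CRT is described as "diminished by 12 weeks of implantation (40), thus data from this time period will be excluded from analysis". The evidence cited concerns CRT. The text then adds procedural recovery and device settling as reasons, but does not say outright that the exclusion covers pacemakers and ICDs.
- CIED remote monitoring: data stay in the device until downloaded "for analysis (for up to 14 months".

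Mean daily PA is taken over the whole dataset. No section gives a common PA window, a minimum number of days or an adjustment for record length. The 12-month look-back under NEHA Episodes: DARS applies to the hospital data, not to PA.

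**The concern.** Range is the maximum minus the minimum, so adding days can only leave it unchanged or widen it. Two people with the same day-to-day variability will have different expected ranges if one has a longer record. IQR and mean absolute deviation do not have this property to any important degree when PA is stationary.

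Individual ranges are therefore not on a common footing when records differ in length. If range is tabulated by subgroup (Descriptive analyses gives frail versus non-frail as an example), a group with more recent implants would show a lower range with no true difference in behaviour. The plan does not say which measure prevails if the three disagree.

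**Working it through.** The plan states no figure for PA variability or for minimum record length, so there is none to reproduce. The check has two steps.

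**Step 1: permitted record lengths**

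- Shortest, if the 12-week exclusion applies to all devices: 26 weeks − 12 weeks = 14 weeks = 98 days.
- Shortest for a non-CRT device, if the exclusion is for CRT only: 6 months ≈ 183 days.
- Longest: 14 × 365.25 / 12 ≈ 426 days.
- Spread: 426 / 98 ≈ 4.3-fold, or 426 / 183 ≈ 2.3-fold.
- Only devices implanted less than about 17 months before download (426 + 84 = 510 days) have less than the maximum record, taking the exclusion as general.

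**Step 2: expected value of each measure by record length**

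The documents give no distribution for daily PA, so the base case is an assumption: independent, normally distributed days with the same SD for everyone. Then

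E(range)/SD = ∫ {1 − Φ(x)ⁿ − [1 − Φ(x)]ⁿ} dx,

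where n is the number of days.

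| Days | E(range)/SD | Ratio to 426 days |
|---|---|---|
| 98 | 5.00 | 0.84 |
| 183 | 5.43 | 0.91 |
| 281 | 5.71 | 0.96 |
| 365 | 5.88 | 0.98 |
| 426 | 5.98 | 1.00 |

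The 281-day row illustrates a download 12 months after implant with 12 weeks removed: 365 − 84 = 281.

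**Sensitivity to the assumption.** Simulations used normal, gamma (shape 2) and lognormal (sigma 0.5) daily PA with day-to-day autocorrelation of 0, 0.3 and 0.6. They also used a normal series in which slow drift made up 20% or 40% of the variance. Ratios of expected values:

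| Measure and comparison | Stationary PA | With slow drift |
|---|---|---|
| Range, 98 v 426 days | 0.74–0.84 | 0.77–0.80 |
| Range, 183 v 426 days | 0.85–0.91 | 0.87–0.89 |
| Range, 365 v 426 days | 0.97–0.99 | 0.98 |
| IQR and mean absolute deviation, 98 v 426 days | 0.98–1.00 | 0.90–0.96 |

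For independent days, the 5th-95th percentile range at 98 days is about 0.98 of its value at 426 days under all three distributions. It was not run with drift.

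**The case against.** The strongest reply is that the plan already holds the remedy. IQR and mean absolute deviation stand beside range, and a disagreement between them would be visible. Being listed first gives range no priority. This stands, and it limits the problem to one of three measures.

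The second reply is that typical records are longer than the minimum. Patients are drawn from annual device follow-up (Screening and recruitment strategy), and Sample Size Calculations counts 150 patient-years for 150 people. At 365 against 426 days the gap is about 2%, and in the 281-day illustration about 4%. This also stands: the 16% and 9% gaps are limits, not expected values. It does not remove the point, because eligibility is six months rather than a year.

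Third, no comparison of range is specified. Descriptive analyses names mean daily PA for basic comparisons and for the analysis of determinants, and mentions subgroup statistics only in general terms. A reader might infer that the frail versus non-frail contrast is biased. The documents do not support that: bias would require time since implant to differ between the groups, and nothing shows that it does.

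A reader might also take the fourfold spread as following from eligibility and device memory alone. Those two give about 2.3-fold. The larger figure needs the 12-week exclusion to apply, and its coverage beyond CRT is not explicit.

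**Conclusion.** The point holds for range, as a minor one. With no common window, the plan as written yields ranges that are not comparable between participants with different record lengths. Under independent normal days, the understatement relative to a 426-day record is about 16% at 98 days, 9% at 183 days and 2% at one year. Skewed or autocorrelated PA raises the 98-day figure to as much as 26%. The direction does not depend on the distribution; the size does, and the documents do not supply one.

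A reader might infer that newer devices will look less variable on every measure, or that Objective 2 is undermined. Neither follows. IQR and mean absolute deviation change by 2% or less between the extremes when PA is stationary. That reassurance is conditional: with the slow drift modelled here they fall by 4–10%, so they are not wholly free of record length either. The share of participants with short records cannot be worked out from the documents.

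**What to change.** In Basic variables from CIED data, either compute range over the same number of days for every participant, stating the number and which days are used, or replace range with the 5th-95th percentile range. Name IQR and mean absolute deviation as the main measures of variability. Report record length overall and by subgroup. State whether the 12-week exclusion applies to all devices or to CRT only, since this sets the shortest record.

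The cost is one redefined derived variable and a few sentences of text. No new data are needed: implant date is already collected (Summary of data to be collected, item 23), and the number of days can be counted from the download. A common window discards some days, but for that measure only. The percentile option keeps all days and leaves a difference of about 2% between the extremes for stationary, independent days.
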